### **5.4. Population of Analysis**

The following patient populations and subsets will be analyzed:

**Table 1: Populations and Subsets of Analysis**

Populations	Subsets
Main Study Period: Part 1	
all-randomized	
safety	
pharmacokinetic	pharmacokinetic (antibody negative subset) pharmacokinetic (antibody positive subset)
Main Study Period: Part 2	
all-randomized	all-randomized (antibody negative subset)
safety	safety – 2 nd treatment course in Main Study Period subset
efficacy	efficacy (antibody negative subset) efficacy (antibody positive subset) efficacy – 2 nd treatment course in Main Study Period subset
pharmacokinetic	pharmacokinetic (antibody negative subset) pharmacokinetic (antibody positive subset) pharmacokinetic – 2 nd treatment course in Main Study Period subset
pharmacodynamic	pharmacodynamic (antibody negative subset) pharmacodynamic – 2 nd treatment course in Main Study Period subset
Extension Study Period	
all-randomized	all-randomized – Extension Study Period subset
safety	safety – Extension Study Period subset
efficacy	efficacy – Extension Study Period subset
pharmacodynamic	pharmacodynamic – Extension Study Period subset

All-randomized, safety and PK populations and its subsets will be defined for the patients from Part 1 and 2, respectively. Efficacy and PD population and its subsets will be defined for the Part 2. Population for Part 2 will include patients from Part 1.

Patients who have any major protocol deviations (as defined in [Section 5.6](#)) may be excluded only from the population (PD and/or Efficacy) that would be affected by the deviation. Patients from the significant GCP non-compliance sites as defined in [Section 5.6](#) will be excluded in all populations.

The number of patients in all populations will be tabulated by the treatment group in each relevant Part and study period. A listing will also be produced, displaying this data.

#### **5.4.1. All-Randomized Population**

The all-randomized population will consist of all patients enrolled and randomly assigned to receive a dose of study drug, regardless of whether or not any study drug dosing was completed. Patients in the all-randomized population and all-randomized population – Extension Study Period subset will be analyzed according to the treatment to which they were randomized in Main Study Period and Extension Study Period, respectively. All general section of Main Study Period (i.e. disposition, demographics, baseline characteristics, etc.) will be based on the all-randomized population. Efficacy data of Main Study Period and Extension Study Period except joint surgery information will be listed for the all-randomized population.

##### **5.4.1.1. All-Randomized (Antibody Negative Subset)**

In the all-randomized population, patients who have “Negative” ADA result at Week 24 will be considered “All-Randomized (Antibody Negative Subset)”.

##### **5.4.1.2. All-Randomized – Extension Study Period Subset**

The all-randomized population – Extension Study Period subset will consist of all patients in the all-randomized population who have received at least one (full or partial) dose of study drug in the Extension Study Period. All general section of Extension Study Period (i.e. disposition, demographics, baseline characteristics, etc.) will be based on the all-randomized population – Extension Study Period subset.

#### **5.4.2. Pharmacokinetic (PK) Population**

The pharmacokinetic population for the Main Study Period will consist of all patients who received two full doses (Week 0 and Week 2) of the study drug and provided at least one post – treatment PK concentration result during the first course of treatment in Main Study Period.

The PK population will be the primary population for the summary of PK data. The analysis of first course period will be based on Part 1 and 2, respectively.

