7.6 Analysis Sets

Five patient populations are defined: PK, efficacy, PD, safety, and all-randomized populations.

The PK population is defined to be all patients who receive at least 2 doses (Week 0 and Week 2) of study drug (CT-P10, Rituxan or MabThera), who provide sufficient blood concentration data to compute the required PK variables, and who do not have any major protocol violation including a violation of the inclusion and exclusion of criteria. The PK population will be the primary population for the summary and analysis of PK data.

The efficacy population is defined to be all patients who receive at least 1 dose of study drug (CT-P10, Rituxan or MabThera), who have at least 1 post-treatment efficacy result, and who do not have any major protocol violation including a violation of the inclusion and exclusion of criteria. The efficacy population will be the primary population for the summary of efficacy data.

The PD population is defined to be all patients receiving at least 1 dose of study drug (CT-P10, Rituxan or MabThera) and providing at least 1 post-treatment PD result. The PD population will be the primary population for the summary of PD data.

The safety population is defined to be all patients who receive at least 1 dose (full or partial) of study drug (CT-P10, Rituxan or MabThera). The safety population will be the primary population for the summary of safety data.

The all-randomized population is defined to be all patients enrolled and randomly assigned to receive a dose of study drug, regardless of whether or not any study drug dosing was completed. All efficacy parameters will also be analyzed for the all-randomized population.

The number of patients, who discontinue from the study prematurely, together with the reasons for discontinuation, will be summarized. In addition, for each analysis population the number of patients will be presented.

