#### **5.4.3. Efficacy Population**

The efficacy population for the Main Study Period will consist of all patients who received at least one full dose (1000 mg) of study drug and provided at least one post-treatment efficacy result during the first course of treatment in Main Study Period.

The efficacy population will be the primary population for the summary of Main Study Period efficacy data.

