#### **5.6. Protocol Deviations**

Protocol deviation will be categorized as “major” or “other (or minor)”. Category of protocol deviation will be identified during the Data Review Meeting (DRM). A major protocol deviation is one that may affect the interpretation of study results or the patient’s rights, safety or welfare. Patients with major protocol deviation could be excluded only from the population (PD and/or Efficacy) that would be affected by the deviation.

Major protocol deviations are defined as follows:

- Mis-randomizations (defined as patients who received the another treatment to which they were assigned at any point during the study)
- Non-compliance of inclusion or exclusion criteria (to be identified by the [REDACTED] medical department via review of data sourced from the site monitoring database)
- Significant GCP non-compliance sites (to be identified by [REDACTED] as sites which have been closed due to suspected scientific misconduct and/or serious GCP non-compliance)
- Receipt of prohibited medication (based on agreement of each as from both [REDACTED] and CLT prior to database lock)

The major protocol deviations and other categories used for exclusion will be summarized for the all-randomized population by study part, treatment group. A listing of major protocol deviations for each patient will also be provided by treatment group.

The significant GCP non-compliance site will be excluded in all populations. The information of this site will be only listed in the Demographics and Treatment-emergent Serious Adverse Events listings, separately.

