### 10.3. Pharmacokinetic Statistical Analysis

In Part 1, the primary PK analysis will assess the similarity of CT-P10, Rituxan and MabThera in terms of  $AUC_{0-last}$ ,  $AUC_{0-\infty}$  and  $C_{max}$  over the first 24 weeks as co-primary PK endpoints.

ANCOVA will be performed for  $AUC_{0-last}$ ,  $AUC_{0-\infty}$  and  $C_{max}$  with treatment group as a fixed effect and country, gender, race, prior anti-TNF- $\alpha$  blocker status (intolerance case versus inadequate response) and RF or anti-CCP status (both positive versus both negative versus either

RF or anti-CCP negative) fitted as covariates. Clinically relevant variables at baseline are used as the covariates for adjusted means. If country is found to be unsuitable as a covariate due to the number of levels, then this may be pooled into a new variable, region (defined as either EU or Non-EU), for use in the statistical model. The  $AUC_{0-last}$ ,  $AUC_{0-\infty}$  and  $C_{max}$  will be natural log transformed prior to the analysis. Point estimates (geometric least squares means and ratios of geometric means) will be calculated by back-transforming the least squares means, and 90% CIs of the ratios (CT-P10 versus Rituxan, CT-P10 versus MabThera, and Rituxan versus MabThera) will be produced.

Similarity will be demonstrated if the 90% CI for the geometric mean ratio of CT-P10 to Rituxan and MabThera in  $AUC_{0-last}$ ,  $AUC_{0-\infty}$  and  $C_{max}$  is within the bounds of 80% and 125%.

When outliers occur at some time points, primary statistical analysis of PK parameters is carried out with data excluding observed outliers. However, a sensitivity analysis will also be performed with data including observed outliers. Additional ANCOVA for the PK primary endpoint will be conducted in patients whose ADA status result at Week 24 is “Negative” both including and excluding outliers. When there are Significant GCP non-compliance sites, an additional sensitivity analysis will be performed for PK primary endpoints.

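### SAP 5.4 and 5.6 leave the PK population out of the major-deviation exclusions that Protocol 7.6 requires for the co-primary PK comparison

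*SAP*

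**What the plan says.** Protocol 7.6, like the synopsis, limits the PK population to patients who received both first-course doses, "who provide sufficient blood concentration data to compute the required PK variables, and who do not have any major protocol violation", and it counts eligibility violations as major. The same condition is placed on the efficacy population. It is not placed on the pharmacodynamic one: "The PD population is defined to be all patients receiving at least 1 dose of study drug (CT-P10, Rituxan or MabThera") and who have a post-treatment PD result.

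SAP 5.4.2 admits to the PK population all patients who "received two full doses (Week 0 and Week 2) of the study drug and provided at least one post"-treatment concentration during the first course. It says nothing about deviations. SAP 5.4.3 is built the same way for efficacy, requiring "at least one full dose (1000 mg) of study drug and provided at least one post-treatment efficacy result during the first course of treatment", and leaves deviations to 5.4 and 5.6.

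Those two sections hold the exclusion rule. SAP 5.4, below its Table 1, says that patients with major deviations "may be excluded only from the population (PD and/or Efficacy) that would be affected by the deviation". SAP 5.6 repeats it: "Patients with major protocol deviation could be excluded only from the population (PD and/or Efficacy) that would be affected by the deviation". SAP 5.6 lists four major categories: mis-randomisation, eligibility non-compliance, sites with significant GCP non-compliance, and prohibited medication. Patients at the GCP sites are removed from every population.

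SAP section 10 runs the PK analyses on the PK population, and 10.3 uses them for the co-primary comparison. Protocol 7.8 requires changes from the planned analyses to be documented in the SAP.

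**The concern.** The two documents define the co-primary PK population differently, and the SAP does not present this as a change. In the SAP, PD means pharmacodynamic (5.4.4) and is a separate set from PK (5.4.2). A programmer who follows the SAP literally would keep patients with major deviations in the PK comparison. The same programmer could remove them from the PD set, which the protocol does not ask for.

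Part 1 is an equivalence comparison, so who belongs in the set should be settled before anyone sees the result. One category also has a known direction of bias. A patient given the other product but analysed as randomised moves the two arms towards each other and favours a finding of similarity. For ineligible patients or prohibited medication the documents give no reason to expect bias in a particular direction. The issue there is only that the analysed set is not the one the protocol promised.

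**Working it through.** **Plan's own Part 1 figure.** Inputs from Protocol 7.5 and SAP 5.2: CV 30%, 50 per arm, bounds 80% to 125%, two one-sided tests at 0.05, true ratio 1.
- Log SD = sqrt(ln(1 + 0.30²)) = 0.2936. Standard error of a pairwise difference = 0.2936 × sqrt(2/50) = 0.0587. Margin = ln 1.25 = 0.2231.
- Normal approximation: 2Φ(0.2231/0.0587 − 1.645) − 1 = 0.969. The t-based value is 0.967. Stated: 96.5%.
- Overall: 1 − 3 × (1 − 0.967) = 0.90. Stated: 90%.
- Drop-out: 50/0.8 = 62.5, so 63 per arm, and 3 × 63 = 189, as stated.

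The sample size reproduces. The point concerns the definition of the set, so no corrected sample size follows from it.

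**Who leaves the PK set, by SAP 5.6 category.**

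| Category | Protocol 7.6 | SAP as written |
|---|---|---|
| Eligibility non-compliance | Excluded, named | No route |
| Mis-randomisation | Excluded if classed as major | No route |
| Prohibited medication | Excluded if classed as major | No route |
| Significant GCP site | Excluded if classed as major | Excluded from all sets |

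Three of the four categories have no route out of the PK set.

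**Is there a backstop?** SAP 10.3 adds PK analyses with and without outliers and in ADA-negative patients. It also says: "When there are Significant GCP non-compliance sites, an additional sensitivity analysis will be performed for PK primary endpoints". None of these addresses the other three categories. SAP 5.4.1 assigns the all-randomised set as randomised and 5.4.5 assigns the safety set by kit number. Neither SAP 5.4.2 nor Protocol 7.6 says how PK patients are assigned.

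**Illustration of swapped product.** The documents give no swap rate, so the counts are assumptions. With k patients swapped in each arm of 50 and analysed as randomised, the expected log difference shrinks by the factor 1 − 2k/50. A true ratio of 1.25 then appears as exp(0.96 × 0.2231) = 1.24 for k = 1 and exp(0.88 × 0.2231) = 1.22 for k = 3.

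The table gives the simulated probability of falsely concluding similarity (400,000 trials per case; one parameter; true CT-P10/Rituxan ratio 1.25; CV 30%; both infusions wrong):

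| Rule | k = 0 | k = 1 | k = 3 |
|---|---|---|---|
| All three pairs (Protocol 7.8.1.1), equal references | 1.2% | 1.7% | 2.9% |
| All three pairs, MabThera midway on the log scale | 4.3% | 5.8% | 9.8% |
| Single pair (not the decision rule) | 5.0% | 6.6% | 11.1% |

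Requiring all three PK parameters to pass would lower these further.

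**The case against.** The strongest reply is that this is a typing error. The protocol places the condition on PK and efficacy, not on PD. SAP 5.4 defines the PD and efficacy sets for Part 2 only, yet 5.6 summarises by study part the deviations used for exclusion. The SAP is based on Protocol 5.1 and declares no change. All of this makes PK the likely intended word. It does not make the text safe to follow: the word is wrong in both operative passages, each says that exclusion is confined to the named sets, and 5.4.2 does not settle the matter.

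A second reply is that Protocol 10.2.2 has patients with significant deviations withdrawn, and a patient withdrawn before the Week 2 infusion cannot have two full doses. That is a real but partial safeguard. Deviations found later leave the patient in the set.

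A third reply concerns bias, and most of it stands. A reader might infer that the SAP inflates the risk of a false similarity claim to around 10%. The documents do not support this. It needs swapped product, analysis as randomised (stated nowhere for PK), a true ratio at the limit and, for the larger figures, either three swaps in each arm with MabThera midway or a single-pair test. Kits are assigned through IWRS or IVRS at randomisation (Protocol 5.4.1). With equal references, the three-pair figures stay below 5%.

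A reader might also infer that the SAP deliberately loosened the PK set. Nothing in the text shows this.

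**Conclusion.** The concern holds as an inconsistency in an operative rule and should be corrected. As written, mis-randomised, ineligible or prohibited-medication patients stay in the co-primary PK comparison if they had two full doses and a post-treatment concentration, unless their site is removed for GCP non-compliance. No sensitivity analysis covers them and the difference from Protocol 7.6 is not documented.

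The size is unknown, because the documents give no deviation counts. The bias argument is secondary: it applies to swapped product only, disappears if patients are analysed by product received, and is nil if the products are identical. The 1.2% to 2.9% range illustrates the mechanism and does not estimate this trial's error rate. That PD is a slip for PK is an inference from the protocol's structure, but the need for a correction does not depend on it.

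**What to change.** In SAP 5.4 and 5.6, name PK in place of PD. In 5.4.2, restore the no-major-violation condition for deviations that affect first-course PK, with the classification settled before unblinding. The limit to the first course matters because SAP 5.6 defines mis-randomisation broadly: "Mis-randomizations (defined as patients who received the another treatment to which they were assigned at any point during the study"). A wrong kit in the second course or the extension cannot change first-course exposure. Since Protocol 7.6 refers to any major violation, this narrowing should itself be recorded under Protocol 7.8. If leaving PK out was intended, document and justify that instead.

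Show the wider set of SAP 5.4.2 as a sensitivity analysis. For that set only, state that patients are grouped by product actually received, from the kit number, with patients who received mixed products left out. In the primary set the grouping rule would have nobody to apply to once first-course mis-randomised patients are excluded.

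The cost is SAP wording, one extra analysis and a somewhat smaller primary PK set, by a number the documents do not give. It should not be assumed that the loss fits within the 13 per arm (63 − 50) allowed for drop-out, because missed doses and unusable profiles draw on the same margin. Protocol 10.2.2 already places deviation decisions before unblinding, and SAP 5.3 fixes the analysis sets before each database is finalised. Because the sponsor is unblinded for the Week 24 report, the classification should be the one made before that point.

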##### **5.4.2.1. Pharmacokinetic (Antibody Negative/Positive Subset)**

In the PK population, patients who show “Positive” result in ADA tests obtained at Week 24 will be considered “Pharmacokinetic (Antibody Positive Subset)”. Other patients who have “Negative” ADA result at Week 24 will be considered “Pharmacokinetic (Antibody Negative Subset)”.

##### **5.4.2.2. Pharmacokinetic – 2nd treatment course in Main Study Period Subset**

The PK population – 2nd treatment course in Main Study Period subset will consist of all patients in the PK population who have received two full doses (Week 24 and Week 26) of study drug and provided at least one post – treatment PK concentration result during the second course of treatment in Main Study Period.

#### **5.4.3. Efficacy Population**

The efficacy population for the Main Study Period will consist of all patients who received at least one full dose (1000 mg) of study drug and provided at least one post-treatment efficacy result during the first course of treatment in Main Study Period.

The efficacy population will be the primary population for the summary of Main Study Period efficacy data.

**5.4.3.1. Efficacy (Antibody Negative/Positive Subset)**

In the efficacy population, patients who show “Positive” result in ADA tests obtained at Week 24 will be considered “Efficacy (Antibody Positive Subset)”. Other patients who have “Negative” ADA result at Week 24 will be considered “Efficacy (Antibody Negative Subset)”.

**5.4.3.2. Efficacy – 2nd treatment course in Main Study Period Subset**

The efficacy population – 2nd treatment course in Main Study Period subset will consist of all patients in the efficacy population who have received at least one full dose (1000 mg) of study drug and provided at least one post-treatment efficacy result during the second course of treatment in Main Study Period.

**5.4.3.3. Efficacy – Extension Study Period Subset**

The efficacy population – Extension Study Period subset will consist of all patients in the efficacy population who have received at least one full dose (1000 mg) of study drug and provided at least one post-treatment efficacy result during the Extension Study Period.

The efficacy population – Extension Study Period subset will be the primary population subset for the summary of Extension Study Period efficacy data.

**5.4.4. Pharmacodynamic (PD) Population**

The pharmacodynamic population for the Main Study Period will consist of all patients who received at least one full dose (1000mg) of study drug and provided at least one post-treatment PD result during the first course of treatment in Main Study Period. The PD population will be the primary population for the summary of PD data.

**5.4.4.1. Pharmacodynamic (Antibody Negative Subset)**

In the pharmacodynamic population, patients who have “Negative” ADA result at Week 24 will be considered “Pharmacodynamic (Antibody Negative Subset)”.

**5.4.4.2. Pharmacodynamic – 2nd treatment course in Main Study Period Subset**

The pharmacodynamic population – 2nd treatment course in Main Study Period subset will consist of all patients in the pharmacodynamic population who have received at least one full dose (1000 mg) of study drug and provided at least one post-treatment PD result during the second course of treatment in Main Study Period.

**5.4.4.3. Pharmacodynamic – Extension Study Period Subset**

The pharmacodynamic population – Extension Study Period subset will consist of all patients in the pharmacodynamic population who have received at least one full dose (1000 mg) of study drug and provided at least one post-treatment PD result during the Extension Study Period.

The PD population – Extension Study Period subset will be the primary population subset for the summary of Extension Study Period PD data.

#### **5.4.5. Safety Population**

The safety population will consist of all patients who received at least one (full or partial) dose of study drug during any dosing period. All patients in the safety population will be analyzed according to the treatment group. Patients receiving at least one dose of CT-P10 during the Main Study Period will be analyzed under the CT-P10 treatment group even the patient ever received Rituxan or MabThera. Otherwise, the treatment group will be determined based on the treatment for the first course.

Treatment received will be based on the kit number recorded on the “Study Treatment Infusion” electronic case report form (eCRF) page. Safety analyses will be conducted based on the safety population.

##### **5.4.5.1. Safety – 2nd treatment course in Main Study Period Subset**

The safety population – 2nd treatment course in Main Study Period subset will consist of all patients in the safety population who have received at least one (full or partial) dose of study drug during the second course of treatment in Main Study Period.

